### 7.2. Covariates and Subgroups

All ANCOVA models will include the baseline value of the variable as a covariate and treatment group as fixed effect with no interaction term.

### 7.3. General Methodology

Descriptive statistics will be provided for all variables in the summary tables by treatment group and overall (except where noted as treatment group only) according to the type of variable summarized.

Quantitative variables will be summarized by using n (sample size), arithmetic mean, SD, median and range (minimum and maximum).

Categorical variables will be summarized by using frequency distributions and percentages.

For the safety analyses, hypothesis testing will be carried out at the alpha = 0.05 level (two-sided) when comparing treatments. P-value will be rounded to three decimal places. Statistical significance will be declared if the rounded p-value will be less than or equal to 0.05.

All data collected in the CRF will be presented in the listings.

### 7.4. Patients Disposition

Disposition of patients will be presented by treatment group and overall for all patients (i.e., the Overall Trial population will be used). The summary will include the number of patients at the Initial Screening Visit, Final Screening Visit, and Day 0 visit (including patients that were not randomized), the number of patients randomized, and the number of patients at each of the remaining visits (Days 6, 7, 13, 14 and 28).

The number of patients included in each of the randomized, safety, ITT, mITT, PP and PK populations will be summarized for each treatment and overall.

The number of patients who completed the study, the number of patients who completed study treatment, and the number of patients who discontinued from the study prematurely after randomization will also be presented by treatment group and overall for the randomized population. This summary will also include a breakdown of the primary reason for discontinuation following the categories on the CRF (i.e., TEAE, withdrawal of consent, lost to follow-up, protocol deviation, study terminated, and other).

Major and minor protocol violations will be presented in the listings only.

### 7.5. Demographic and Screening/Baseline Characteristics

The demographic and screening/baseline characteristics will be summarized by treatment group and overall by means of descriptive statistics.

The following characteristics will be provided for the Safety population:

- Age (years)
- Sex (male/female)
- Race (white, black, Hispanic, native American, Asian, other)
- Weight (kg) at Initial Screening Visit and Day 0 (prior to study drug administration)
- Height (cm) at Initial Screening Visit
- BMI (kg/m^2) at Initial Screening Visit
- Pulse rate (beats/min) at Initial Screening Visit
- Respiration rate (breaths/min) at Initial Screening Visit

- Oral body temperature (degrees Celsius) at Initial Screening Visit
- Resting SBP and DBP determined as part of manual vital signs at Initial Screening Visit (average of 3 recordings for left and right arm) and at Day 0 (average of 3 recordings for the arm with the higher average resting SBP determined as part of the manual vital signs at the Initial Screening Visit)
- ECG result at Initial Screening Visit (normal, abnormal NCS, abnormal CS, no result)
- SBPday, SBPnight, SBP24h, DBPday, DBPnight and DBP24h at baseline (Day -1 to Day 0)

### **Past disease and concomitant disease**

Past and concomitant diseases will be coded using MedDRA dictionary (version 19.1) and frequency distributions and percentages will be summarized by treatment group for the safety population by SOC and PT.

Counts will be given for both SOC and PT by subject. Subjects experiencing more than one past disease (or concomitant disease) event within a given SOC category will be counted only once within that SOC. Similarly, subjects experiencing more than one past disease (or concomitant disease) event fitting a given PT will be counted only once for that PT.

### **Previous, concomitant, posterior, and unclassified medications**

Medications will be coded using WHO-DD, September, 2016, using the following ATC codes:

- Anatomical Main Group (ATC 1st level code);
- Chemical subgroup (ATC 4th level code);
- Preferred name.

Previous, concomitant, posterior, and unclassified medications (as defined in Section 1.3.16) will be summarized separately for the Safety population by anatomical main group, chemical subgroup and preferred name by treatment group.

Subjects experiencing more than one previous (or concomitant or posterior or unclassified) medication within the same anatomical main group or chemical subgroup will be counted only once for that group. Similarly, subjects experiencing more than one previous (or concomitant or posterior or unclassified) medication with the same preferred name will be counted only once for that preferred name.

No formal (hypothesis testing) comparisons between treatments on baseline characteristics will be done.

### **7.6. Treatment Compliance and Extent of Exposure**

Treatment compliance and extent of exposure as defined by the 7 parameters summarized in Section 5 will be summarized using descriptive statistics by treatment group and overall for the Safety population.

### **7.7. Primary Efficacy Analysis**

The primary efficacy analysis is to establish the non-inferiority of amlodipine tablets (10 mg) and celecoxib capsules (200 mg) given together (arm 1) with half the effect achieved with amlodipine tablets (10 mg) given alone (celecoxib placebo) (arm 2).

Statistics are based on the change in BP from the baseline ABPM measurement (Day -1 to Day 0) to the post-dose ABPM measurement (Day 13 to Day 14 or if a LOCF is required Day 6 to Day 7), as this represents the efficacy of the treatment. As indicated below, the change will be Day 13 to Day 14 minus Baseline and so a reduction will be a negative number. Sensitivity analysis will compare the results for the ITT population with those of the PP dataset and an MMRM analysis, if possible. A sensitivity analysis will also compare the results with the mITT population.

The hypothesis test being conducted is as follows:

$$H_0: \Delta SBP_{day,1} - 0.5(\Delta SBP_{day,2}) \geq 0 \text{ mmHg}$$

$$H_1: \Delta SBP_{day,1} - 0.5(\Delta SBP_{day,2}) < 0 \text{ mmHg}$$

Where  $\Delta SBP_{day,1}$  is the change, for subjects in arm 1, in the  $SBP_{day}$  from the baseline ABPM measurement ( $SBP_{day,1,base}$ ) to the final ABPM measurement ( $SBP_{day,1,14}$ ).

$$\Delta SBP_{day,1} = SBP_{day,1,14} - SBP_{day,1,base}.$$

$\Delta SBP_{day,2}$  is the change, for subjects in arm 2, in  $SBP_{day}$  from the baseline ABPM measurement ( $SBP_{day,2,0}$ ) to the final ABPM measurement ( $SBP_{day,2,14}$ ).

$$\Delta SBP_{day,2} = SBP_{day,2,14} - SBP_{day,2,base}.$$

This makes the actual test statistic:

$$\delta = \Delta SBP_{day,1} - 0.5(\Delta SBP_{day,2})$$

A one-sided 97.5% CI for  $\delta$  will be computed. In addition, a two-sided non-inferiority t-test comparing  $\delta$  to 0 will provide an appropriate p-value. This p-value will be computing the probability of observing a value  $\geq 0$  from a normal distribution for  $\delta$ .

Refer to the protocol Appendix H for further details regarding the efficacy analysis, and in particular the non-inferiority margin.

## 7.8. Secondary Efficacy Analysis

Per the protocol, a serial gatekeeping strategy was to be used to evaluate the effect of amlodipine tablets (10 mg) and celecoxib capsules (200 mg) given together on the secondary efficacy endpoints. If and only if the statistical significance was achieved for the primary efficacy endpoint, the secondary hierarchical analysis was to be used to evaluate the secondary endpoints (i.e., body weight,  $SBP_{24h}$ ,  $DBP_{24h}$ , and creatine clearance) and was only to proceed to the next endpoint in the list if the alpha is met for the prior analyses. While defining success at the secondary efficacy level will remain based on the hierarchical approach, regardless of the outcome, all four secondary efficacy endpoints (body weight,  $SBP_{24h}$ ,  $DBP_{24h}$ , and creatine clearance) will be analyzed for informational purposes and to allow comparisons to the trends and statistically significant differences observed in the prior trial (KIT-302-03-01).

For all secondary efficacy endpoints, the mean change has been computed considering the difference between the value at endpoint (Day 13 to Day 14 for ABPM endpoints and Day 14 for body weight and creatinine clearance) and the value at baseline (Day -1 to Day 0 for ABPM endpoints and Day 0 pre-dose for body weight and creatinine clearance) [Endpoint – Baseline].

1. Analysis of Variance (ANOVA) will be used to compare the changes in body weight among the three treatment arms. The omni-bus test will conclude if any differences exist with post-hoc comparisons identifying specific differences between treatment arms. Any statistically significant differences will be sufficient to pass this gate in the study-wide gate keeping strategy.

$$H_0: \Delta BW_1 = \Delta BW_2 = \Delta BW_3$$

$$H_1: \text{At least one difference, } \Delta BW_i - \Delta BW_j \neq 0$$

Where  $\Delta BW_1$  is the change, for subjects in arm 1, in body weight from the baseline measurement to the post-treatment measurement.  
 $\Delta BW_2$  is the change, for subjects in arm 2, in body weight from the baseline measurement to the post-treatment measurement.  
 $\Delta BW_3$  is the change, for subjects in arm 3, in body weight from the baseline measurement to the post-treatment measurement.

2. A two-sample t-test for superiority will be used to test the one-sided hypothesis that treatment with amlodipine tablets (10 mg) and celecoxib capsules (200 mg) given together (arm 1) lowers SBP24h to a greater degree than amlodipine tablets (10 mg) given alone (with matched celecoxib placebo) (arm 2).

$$H_0: \Delta SBP_{24h,1} - \Delta SBP_{24h,2} = 0$$

$$H_1: \Delta SBP_{24h,1} - \Delta SBP_{24h,2} > 0$$

Where  $\Delta SBP_{24h,1}$  is the change, for subjects in arm 1, in SBP24h from the baseline ABPM measurement to the post-treatment ABPM measurement.

$\Delta SBP_{24h,2}$  is the change, for subjects in arm 2, in SBP24h from the baseline ABPM measurement to the post-treatment ABPM measurement.

3. A two-sample t-test for superiority will be used to test the one-sided hypothesis that treatment with amlodipine tablets (10 mg) and celecoxib capsules (200 mg) given together (arm 1) lowers DBP24h to a greater degree than amlodipine tablets (10 mg) given alone (with matched celecoxib placebo) (arm 2).

$$H_0: \Delta DBP_{24h,1} - \Delta DBP_{24h,2} = 0$$

$$H_1: \Delta DBP_{24h,1} - \Delta DBP_{24h,2} > 0$$

Where  $\Delta DBP_{24h,1}$  is the change, for subjects in arm 1, in DBP24h from the baseline ABPM measurement to the post-treatment ABPM measurement.

$\Delta DBP_{24h,2}$  is the change, for subjects in arm 2, in DBP24h from the baseline ABPM measurement to the post-treatment ABPM measurement.

4. A two-sample t-test for superiority will be used to test the one-sided hypothesis that treatment with amlodipine tablets (10 mg) and celecoxib capsules (200 mg) given together (arm 1) improves creatinine clearance to a greater degree than amlodipine tablets (10 mg) given alone (with matched celecoxib placebo) (arm 2).

Note: an improvement in creatinine clearance is assumed to be an increase in creatinine clearance; therefore, a positive difference is an indication of improvement as shown in the following hypotheses.

$$H_0: \Delta CC_1 - \Delta CC_2 = 0$$

$$H_1: \Delta CC_1 - \Delta CC_2 > 0$$

Where  $\Delta CC_1$  is the change, for subjects in arm 1, in creatinine clearance from the baseline creatinine clearance to the post-treatment creatinine clearance.

$\Delta CC_2$  is the change, for subjects in arm 2, in creatinine clearance from the baseline creatinine clearance to the post-treatment creatinine clearance.

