10.2.2 BP Change Comparisons

Statistics are based on the reduction in BP from the baseline ABPM measurement (Day –1 to Day 0) to the post-dose ABPM measurement (Day 13 to Day 14 or if a LOCF is required Day 6 to Day 7), as this represents the efficacy of the treatment. Reductions will be, therefore, represented by positive numbers and increases by negative numbers. For this reason, the change in BP from baseline to final ABPM measurement will be a paired subtraction of the final ABPM measurement from the baseline ABPM measurement. Sensitivity analysis will compare these results with those of the PP dataset and an MMRM analysis.

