### **1.3.7. Definition of change from baseline**

For all efficacy endpoints, the mean change will be computed considering the difference between the value at endpoint and the value at baseline (Endpoint minus Baseline). The protocol states the mean change as baseline minus endpoint. This change does not affect the absolute value of the results but gives a more intuitive interpretation of the direction of change (i.e., with a negative value indicating a decrease in BP over time and a positive value indicating an increase in BP over time).

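### SAP 7.8 prints the one-sided alternatives for SBP24h and DBP24h in the wrong direction for the SAP's own coding of change

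*SAP*

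**What the plan says.** **Coding of change.** SAP 1.3.7 replaces the protocol's baseline-minus-endpoint difference with endpoint minus baseline for all efficacy endpoints, "with a negative value indicating a decrease in BP over time and a positive value indicating an increase in BP over time". SAP 7.8 repeats the rule for the secondaries: "For all secondary efficacy endpoints, the mean change has been computed considering the difference between the value at endpoint" and the value at baseline, with the order stated in brackets as endpoint minus baseline. SAP 7.7 applies the same coding to the primary: "the change will be Day 13 to Day 14 minus Baseline and so a reduction will be a negative number".

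**The tests.** SAP 7.8 items 2 and 3 each specify a one-sided two-sample t-test for superiority. In words, the hypothesis is that arm 1 lowers SBP24h (item 2) or DBP24h (item 3) "to a greater degree than amlodipine tablets (10 mg) given alone (with matched celecoxib placebo) (arm 2". The printed alternatives are "H_1: \Delta SBP_{24h,1} - \Delta SBP_{24h,2} > 0" and "H_1: \Delta DBP_{24h,1} - \Delta DBP_{24h,2} > 0". In both items the delta is defined as the change from the baseline to the post-treatment ABPM measurement.

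**Item 4, creatinine clearance.** The same inequality is printed, with a note that an increase is an improvement, so that "a positive difference is an indication of improvement as shown in the following hypotheses".

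**Protocol.** Section 10.2.5 prints the same two blood pressure alternatives, under the convention of section 10.2.2: "Reductions will be, therefore, represented by positive numbers and increases by negative numbers".

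**The concern.** Each of the two items states two opposite one-sided tests, one in words and one in symbols. In a one-sided test the direction decides the result.

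SBP24h and DBP24h are the second and third secondary endpoints in the hierarchy, and creatinine clearance comes after them. A program that follows the words tests correctly. A program that follows the symbols could almost never credit a true blood pressure benefit at either step, and creatinine clearance could then not be formally reached.

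SAP 1.1 says the study was designed to confirm the enhanced antihypertensive effect and the renal effect seen in the prior study, so these endpoints carry weight.

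**Working it through.** **1. Sign check.** With Δ = endpoint − baseline, a larger fall in arm 1 means Δ₁ < Δ₂, so Δ₁ − Δ₂ < 0. Example with the prior study's SBPday means (Protocol Appendix H.1): −10.6 − (−8.8) = −1.8. This is a benefit for the combination, and it lies outside the printed alternative.

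| Place | Coding of change | Printed H1 | Consistent? |
|---|---|---|---|
| Protocol 10.2.5, SBP24h and DBP24h | reduction positive | > 0 | yes |
| SAP 7.7, primary | endpoint − baseline | < 0 | yes |
| SAP 7.8 item 2, SBP24h | endpoint − baseline | > 0 | **no** |
| SAP 7.8 item 3, DBP24h | endpoint − baseline | > 0 | **no** |
| SAP 7.8 item 4, creatinine clearance | endpoint − baseline, increase is good | > 0 | yes |

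Reading the delta as a reduction does not rescue items 2 and 3. They call it the change, and the opening of 7.8 fixes the order of subtraction. Only the protocol synopsis defines the delta as a reduction, and SAP 1.3.7 replaces that coding.

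**2. Illustration of size.** The error itself needs no numbers. The documents give no 24-hour means or SDs, so the prior study's day and night values from Appendix H.1 stand in for them.

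- Appendix H.4 gives n = 45 per arm.
- One-sided 0.025 (z = 1.960) is an assumption. SAP 7.8 states no level for the secondaries.
- s = √((s₁² + s₂²)/2), and SE = s·√(2/45).
- Power as intended is Φ(d/SE − z). Power as printed is 1 − Φ(d/SE + z). Here d is the true extra reduction in arm 1.

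| Proxy | d (mmHg) | s₁, s₂ | SE | Intended | Printed |
|---|---|---|---|---|---|
| SBPday | 10.6 − 8.8 = 1.8 | 9.2, 8.1 | 1.83 | 16.5% | 0.16% |
| SBPnight | 10.5 − 6.4 = 4.1 | 10.6, 11.4 | 2.32 | 42.3% | 0.010% |
| DBPday | 7.5 − 5.5 = 2.0 | 6.4, 5.1 | 1.22 | 37.4% | 0.016% |
| DBPnight | 7.0 − 3.2 = 3.8 | 8.6, 7.8 | 1.73 | 59.3% | 0.002% |

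For SBPday, d/SE = 0.985. Then Φ(0.985 − 1.960) = 16.5% and 1 − Φ(0.985 + 1.960) = 0.16%. A noncentral t calculation on 88 df gives 0.17% for the largest printed value and moves the intended values by less than one percentage point.

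**3. Sensitivity to the assumptions.** At one-sided 0.05 (z = 1.645) the intended values are 25.5% and 54.9% for the SBP proxies and 49.8% and 70.9% for the DBP proxies. The largest printed value is 1 − Φ(0.985 + 1.645) = 0.43%. SAP 3.2 reports a final allocation of 6:6:1. With about 105 subjects that gives 105 × 6/13 ≈ 48 per arm, which changes little: the SBPday proxy becomes 17.3% intended and 0.15% printed.

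**4. Requiring the primary to succeed first.** The primary contrast has mean 10.6 − 0.5 × 8.8 = 6.2 and SE √((9.2² + 0.25 × 8.1²)/45) = 1.50. It passes with probability Φ(6.2/1.50 − 1.960) = 98.5%. With an assumed correlation of 0.7 to 0.9 between daytime and 24-hour changes (bivariate normal), success on both the primary and SBP24h stays at 16.5% (day proxy) and 42.3% (night proxy) as intended. It is at most 0.083% as printed. Body weight, the step between them, is not modelled because no weight data are given. It can only lower these figures. Formal success on DBP24h cannot exceed that on SBP24h.

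**The case against.** The strongest reply is that this is a slip of notation whose meaning nobody would mistake. Each formula follows a sentence that gives the direction. SAP 2.2 and 2.4 speak of the mean reduction. SAP 2.3 notes, for the primary, that a negative value favours arm 1, and 7.7 prints its alternative as below zero. SAP 8.2 provides for double programming. SAP 7.8 also has all four secondaries analysed whatever the hierarchy shows, so no estimate is lost. The harm therefore depends on a programmer following one symbol against the text around it.

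Most of this stands as a limit on the consequences. The intent is recoverable, the programmed direction is unknown, and only formal success status is at risk. It does not remove the error. The note in SAP 2.3 sits under the primary endpoint and does not cover items 2 and 3. Quality control compares programs with the analysis plan, and here the plan states both directions, so agreement with the plan cannot settle which is right.

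Three smaller points are also fair. The power figures rest on proxies and on a level the SAP does not state for these tests, so they are illustrative only. Writing the null as an equality is not wrong for a one-sided test. Redefining the change as baseline minus endpoint within items 2 and 3 would cure the contradiction equally well, although it would break the single coding that 1.3.7 sets for all efficacy endpoints.

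**Conclusion.** The concern holds. Under the SAP's own coding, the printed alternatives for SBP24h and DBP24h state the reverse of the hypotheses given in words, and nothing in the SAP exempts them. They are a carry-over from the protocol, missed when the coding was reversed. The primary hypotheses and the creatinine clearance hypotheses are correct as printed.

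This rests on the text alone. The size figures rest on the assumptions listed above, but under either significance level considered the printed rule has well under a 1% chance of crediting a true benefit. The documents do not show that any test was run in the wrong direction. The plan should be corrected because direction is decisive in these two tests and because SAP 1.5 lists the current version, v4.0, as post-unblinding. An unresolved direction in such a document invites the question of when it was settled.

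**What to change.** - In SAP 7.8 items 2 and 3, print H0: Δ₁ − Δ₂ ≥ 0 and H1: Δ₁ − Δ₂ < 0, with Δ as endpoint minus baseline, in the same form as 7.7. Keeping the null as an equality is acceptable. The direction of H1 is what must change.
- Add a direction note to each item, like the one in item 4, saying that a negative difference favours arm 1. Leave item 4 unchanged.
- Record in SAP 1.3 which direction SAP v3.0 (October 12, 2017, pre-unblinding) stated and which direction the programs used, after checking the programs.
- Optionally, state the one-sided significance level for the secondary tests in 7.8. One-sided 0.025 is given for the sample size (1.3.11 and 3.1) and is implied for the primary by the one-sided 97.5% interval (1.3.5 and 7.7). It is not stated for the secondaries.

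The cost is two hypothesis pairs, two short direction notes, one documentation entry and a check of the programs. Data, type of test, hierarchy and sample size stay as they are.

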## 7.9. Safety Analysis

### AEs

PTAEs and TEAEs will be presented separately.

All AE analyses will use the Safety population. The AE listings will use the Randomized population.

See section 6.4 for AE definitions. Refer to Section 1.3.9, bullet d for further detail regarding how the PI assignments of expectedness differed from the protocol-specified definition and how this will be handled.

A summary of TEAE categories [all TEAEs, treatment emergent SAEs, ADRs, oedema events, other PTs of interest, treatment emergent UAEs, TEAEs leading to discontinuation, and TEAEs leading to death] by number of events within the category and the number and percentage of patients experiencing an event in that category will be tabulated by treatment group. Differences between groups will be evaluated using Chi-square test or Fisher's exact test (if more than 20% of the cells in a contingency table have expected counts less than 5).

AEs will be coded using the MedDRA dictionary (version 19.1). The incidence of all TEAEs will be tabulated by SOC, PT, severity and patient identification. The number of events and the number and percentage of patients with at least one event will be presented. Subjects experiencing more than one TEAE within a given SOC category will be counted only once for that SOC. Similarly, subjects experiencing more than one TEAE fitting a given PT will be counted only once for that PT. If a PT is reported more than once for a given subject, the greatest severity will be presented in the summary table.

The severity of AEs were graded as 1, 2, 3, or 4 according to WHO Toxicity Criteria (see Appendix C of protocol), or if the AEs were not included in this toxicity grading scale, they were categorized as mild, moderate, or severe per the definitions in Section 8.1.2 of the protocol. To allow for tabular summaries of severity, AEs assigned as grade 1 or mild will be included under mild, AEs assigned as grade 2 or moderate will be included under moderate, and AEs assigned as grade 3 or 4 or severe will be included under severe. Mild, moderate, and severe row headers will be presented under each PT, except in the case where there were no AEs across all treatment groups fitting a severity classification for that PT, in which case that severity classification will not be included as a row under that PT.

Similar tabular summaries will be produced for each of the following: treatment emergent SAEs, ADRs, oedema events, other PTs of interest, treatment emergent UAEs, TEAEs leading to discontinuation, PTAEs, PTAEs leading to discontinuation, and pre-treatment SAEs. In the case of the latter two, the summaries will not be produced if there are no PTAEs leading to discontinuation or pre-treatment SAEs, respectively. For the ADR summary, if an ADR is reported more than once for a given subject, the worst-case attribution will be presented in the summary table.

A comparison of TEAE rates between the amlodipine + celecoxib and amlodipine + placebo arms will be performed using an exact logistic regression model with the TEAE ("1"=At least one TEAE occurred for the patient; "0"=otherwise) as dependent variable and treatment (amlodipine + celecoxib and amlodipine + placebo) as fixed effects. The probability modeled will be TEAE="1". The number of patients and the number of patients considered in the model will be provided. The exact odds ratio of the fixed effects will be calculated (amlodipine + celecoxib and amlodipine + placebo) with the relative 95% CI and p-value.

The same model will be repeated by considering treatment-emergent SAE (“1”=At least one treatment-emergent SAE occurred for the patient; “0”=otherwise) as dependent variable, with the caveat that if no treatment-emergent SAEs are reported the table will not be produced.

The rates of oedema events between the amlodipine + celecoxib arm and the amlodipine + placebo arm will be compared using an exact logistic regression and reporting the odds ratio. Oedema event (1 = at least one TEAE with PT of oedema, oedema peripheral, peripheral swelling, swelling, or joint swelling occurring for the subject; 0 = otherwise) will be the dependent variable, and treatment (amlodipine + celecoxib and amlodipine + placebo) will be the fixed effects.

The Fisher’s exact test will be run to compare the number of oedema events that occurred while on treatment (Day 0 to Day 14+1) and post-treatment (>Day 14+1) between treatment arms 1 and 2 (amlodipine + celecoxib and amlodipine + placebo).

